3.2 Study design rationale

This study is designed as an open-label, single arm, proof of concept study in order to determine the appropriate emapalumab dosing regimen neutralizing IFN γ in patients at risk of GF prior to initiating a pivotal study.

An open label, single arm design is considered appropriate given the life-threatening condition of the patient population and due to the early stage of development of emapalumab in this indication. The proposed treatment strategy is not an alternative to current treatments, therefore patients will receive the same standard of care as if they were not enrolled in the study.

Patients receiving HSCT at high risk of GF will be included in the study to ensure patients with highest unmet need are included. Only patients presenting CXCL9 levels above a defined threshold and an ANC below 500 cells/ μ L will be eligible to receive emapalumab treatment for primary GF. Patients with CXCL9 above threshold will also be eligible to receive emapalumab based on treating physician's decision in case of signs of secondary graft failure (i.e. donor chimerism drop of at least 10% for 2 consecutive measurements and/or ANC below 500

cells/ μL and/or thrombocytopenia below 30000/ μL not explained by any other reason than potential graft rejection) during the extended monitoring period.

CXCL9 elevation is observed several days prior to any clinical signs of primary GF and provides the opportunity of a biomarker driven pre-emptive treatment approach and to initiate early treatment to inhibit the deleterious activity of IFN γ on the graft. In case of secondary GF, preliminary observations have shown an elevation of CXCL9, a few days before GF or concomitantly (see section 1.1.2 and IB). This preliminarily observed difference of CXCL9 elevation time prior to GF justifies the need to consider pre-emptive treatment of secondary GF as optional based on medical judgment.

For the above mentioned reasons, each study cohort completion is based on the recruitment of the required number of evaluable patients treated for primary GF (see sample size section 12.1). Given that similar PK/PD profile of emapalumab is expected in patients treated to pre-empt primary and secondary GF, data obtained in the secondary GF patients may be used to inform dose decision for the subsequent cohorts.

Patients with CXCL9 levels below threshold will be monitored and will enter follow up for non-emapalumab treated patients at the end of the monitoring periods. This additional group of patients will allow to confirm the frequency of GF when CXCL9 levels are below threshold.

In clinical practice, GF is usually not confirmed until at least day 21 and up to 42 days following HSCT, therefore the monitoring period for primary GF will last up to 42 days. As soon as an ANC is ≥ 500 cells/ μL , patients will enter the extended monitoring period for secondary GF which will last up to 98 days. ANC increase can occur within 10 days after HSCT, but may take up to 30-40 days, mostly depending on the source of stem cells. Secondary GF, which may occur after initial engraftment, is usually observed within the first few months after transplant, therefore the extended monitoring will last up to 98 days.

To achieve rapid IFN γ neutralization, an initial dose of 6 mg/kg emapalumab will be administered. To maintain further IFN γ neutralization covering the duration of engraftment, emapalumab administration will be continued at a dose of 3 mg/kg after 3 days (second infusion) and every 3 or 4 days thereafter until stable engraftment has been achieved or until a maximum of 15 doses. This definition of treatment duration will guarantee that patients are treated until the graft has clearly engrafted but not beyond. Further details on the dose regimen rationale can be found in section 5.3.

Patients treated pre-emptively for secondary graft failure will receive the same dose regimen as patients treated pre-emptively for primary graft failure in the 3 cohorts.

Patients will be followed up until 3 years post HSCT in order to collect survival data, occurrence of GvHD and use of defined treatments or procedures to support the graft function post-transplant.

Patients will be stratified at screening into two groups in order to include at least 40% malignant and 40% non-malignant. Stratification will allow to explore the appropriate dose inhibiting IFN γ production in a similar number of patients presenting malignant or non-malignant disease in each cohort. Patients below 1 year are considered more vulnerable and will therefore not be included in the study until the safety has been confirmed in patients 1 year or older.

3.3 Transition between cohorts

- After the last patient of each cohort (cohort 1, 2 or 3) has completed emapalumab treatment for primary GF (4 evaluable patients), patient screening will be put on hold until data will be analyzed.
- Patients in monitoring or extended monitoring periods (at the time the Sponsor will communicate that screening is on hold) will proceed to the EoS visit and thereafter transition to the follow-up period (for non-emapalumab treated patients) and receive treatment as per medical practice.
- Patients in treatment phase for primary or secondary GF will continue to be treated as per protocol.
- The Sponsor will communicate to the investigators any decision on the dose regimen to be adopted to the next cohort or if additional patients will be added to the same cohort (rules described in section 12.2).
- Screening will be resumed once the Sponsor confirms that the study will enroll additional patients in the same dose cohort or if an additional cohort will be initiated with dose regimen adaptations.

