3.4.5 Follow-Up Period

Assessments to be performed during the follow-up period are detailed in the Schedule of Assessments (Table 7a and Table 7b). The follow-up period will last 3 years from the HSCT date for both patients who received and those who did not receive emapalumab, as detailed below.

Follow-up period: emapalumab treated patients

All emapalumab treated patients will enter the follow-up period:

- (i) Upon completion of treatment or engraftment, whichever comes first
- (ii) In case of premature treatment discontinuation for any reason

The follow-up period for patients who received emapalumab will consist of 6 visits: at 1 week \pm 2 days, 2 weeks \pm 2 days, 4 weeks \pm 2 days, 8 weeks \pm 1 week, 12 weeks \pm 1 week and 24 weeks \pm 2 weeks after last study drug administration (EoS visit) and 3 phone calls for survival observation at 1, 2 and 3 years after HSCT.

During the survival calls defined concomitant medications/procedures (i.e. any HSCT, blood product transfusion, stem cell boost, DLI or hematopoietic agents) and occurrence of GvHD since previous visit/call should be recorded.

The first follow-up visit will be 1 week \pm 2 days after last study drug administration or 1 week after EoT (in case of treatment discontinuation or engraftment before the last dosing day).

Follow-up period: non-emapalumab treated patients

In case treatment with emapalumab has not been initiated, patients will undergo an EoS visit (within 1 week from the last day in the monitoring periods) and enter the phone calls follow-up.

A patient can enter follow-up in the following occasions:

- (i) At the end of the monitoring (Day 42) or extended monitoring (Day 98).
- (ii) If they require a second HSCT anytime during the monitoring periods.
- (iii) If any prohibited medication is taken during the monitoring periods.
- (iv) In case of re-occurrence of malignant disease, GvHD diagnosis, uncontrolled infection or clinical manifestations of infections representing exclusion criteria at time of eligibility to treatment.

The follow-up period for non-emapalumab treated patients will consist of 4 phone calls at 6 months, 1, 2 and 3 years after HSCT. During the survival calls defined concomitant medications/procedures (i.e. any HSCT, blood product transfusion, stem cell boost, DLI or hematopoietic agents) and occurrence of GvHD since previous visit/call should be recorded.

End of Study Visit

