Assessments to be performed during the EoS visit are detailed in the Schedule of Assessments (Table 7a and Table 7b).

- For emapalumab treated patients, the EoS visit correspond to the last follow-up visit (Follow-up visit 6) at week 24 \pm 2 days from last study drug administration.
- Non-emapalumab treated patients will require to attend the EoS visit within 1 week from the last day in the monitoring periods.

Table 2 Transition between periods in case of ANC < 500 cells/ μ L during the monitoring period

Monitoring	Treatment	Follow-up For emapalumab treated patients	Follow-up For non-emapalumab treated patients
CXCL9 above threshold + ANC <500 cells/ μ L 	Enter treatment period		Perform EoS visit and enter phone-calls follow-up period:
CXCL9 below threshold + ANC <500 cells/ μ L  Continue monitoring ✓ Unless a second HSCT is required ✓ As soon as ANC \geq 500, transition to extended monitoring Table 3		Enter follow-up period: ✓ Upon completion of treatment or engraftment during treatment, whichever comes first ✓ Upon premature treatment discontinuation for any reason	
 ✓ At the end of monitoring or ext monitoring period ✓ In case of re-occurrence of malignant disease, GvHD diagnosis, uncontrolled infection or clinical manifestations of infections representing exclusion criteria at time of treatment ✓ If a second HSCT is required ✓ If any prohibited med is taken during the monitoring periods

Table 3 Transition between periods in case of ANC \geq 500 cells/ μ L during the monitoring period

Monitoring	Extended Monitoring	Treatment	Follow-up For emapalumab treated patients	Follow-up For non-emapalumab treated patients
As soon as ANC \geq 500 cells/ μ L during monitoring, enter extended monitoring	CXCL9 above threshold + Signs of sGF 	Enter treatment period	Enter follow-up period: ✓ Upon completion of treatment or engraftment during treatment, whichever comes first	Perform EoS visit and enter phone-calls follow-up period: ✓ At the end of monitoring or ext monitoring period ✓ In case of re-occurrence of malignant disease, GvHD diagnosis, uncontrolled infection or clinical manifestations of infections representing exclusion criteria at time of treatment
	If CXCL9 below threshold Continue extended monitoring unless a second HSCT is required		✓ Upon premature treatment discontinuation for any reason	
 ✓ If a second HSCT is required ✓ If any prohibited med is taken during the monitoring periods

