7.1 Efficacy

- Occurrence of primary GF from HSCT up to EoS visit.
- Occurrence of secondary GF from HSCT up to EoS visit.
- Occurrence of primary or secondary GFs from HSCT up to EoS visit.
- Occurrence of mixed donor chimerism <10% and <20% (based on unselected leukocytes or sorted T cells) from HSCT up to EoS visit.
- Occurrence of received transfusion of blood products due to poor graft function, hematopoietic growth factors, stem cell boost or DLI from HSCT up to 3 years follow up.
- Occurrence of receiving an additional allogeneic HSCT from HSCT up to 3 years follow up.
- Occurrence of poor graft function from HSCT up to EoS visit.
- Occurrence of event free engraftment from HSCT up to 3 years follow up.
- Occurrence of GvHD from HSCT up to 3 years follow up.
- Occurrence of engraftment syndrome from HSCT up to EoS visit.
- Occurrence of endothelial complications from HSCT up to EoS visit.
- Overall survival from HSCT up to 3 years follow up.

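### Screening holds and prohibited-medication exits cut GF observation short in untreated patients, so the crude GF frequency below the CXCL9 threshold is biased low

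*Combined protocol and SAP*

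**What the plan says.** Section 3.2 gives the untreated patients a purpose: "This additional group of patients will allow to confirm the frequency of GF when CXCL9 levels are below threshold". It also says how long GF takes to show itself. For primary GF, "GF is usually not confirmed until at least day 21 and up to 42 days following HSCT". Secondary GF is expected within the first few months, "therefore the extended monitoring will last up to 98 days".

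Section 3.3 puts screening on hold after the last patient of a cohort (1, 2 or 3) has completed treatment for primary GF. At that point "Patients in monitoring or extended monitoring periods (at the time the Sponsor will communicate that screening is on hold) will proceed to the EoS visit", followed by telephone follow-up. Patients already on emapalumab carry on. Section 3.4.5 lists further routes out of monitoring, including this one: "If any prohibited medication is taken during the monitoring periods". On timing, it says "Non-emapalumab treated patients will require to attend the EoS visit within 1 week from the last day in the monitoring periods".

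The GF endpoints in Section 7.1 stop at that visit, for example "Occurrence of primary or secondary GFs from HSCT up to EoS visit". Afterwards, "The follow-up period for non-emapalumab treated patients will consist of 4 phone calls at 6 months, 1, 2 and 3 years after HSCT". Tables 7a and 7b schedule GF recording at visits but not at the calls. The calls collect survival, GvHD, any HSCT, transfusion, stem cell boost, DLI and hematopoietic agents.

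Section 12.5 summarises categorical data by counts and percentages. Section 12.5.6 uses observed data without imputation. No section states a censoring rule, a minimum follow-up or a time-to-event estimator for GF in untreated patients.

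**The concern.** A patient at Day 5 when the hold is announced has a last GF assessment by about Day 12. The protocol itself says GF is not usually confirmed that early. If the patient stays in the denominator of a crude percentage with no GF recorded, the patient contributes to the frequency exactly as someone observed free of GF to Day 42 would.

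The error has one direction. It lowers the apparent GF frequency below threshold and so makes CXCL9 look better at ruling out GF than it is. Its size would depend on accrual speed and hold dates, which have nothing to do with the marker. At stake are the stated reason for following this group and the exploratory objective on CXCL9 and GF risk, which is tied to a diagnostic test.

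**Working it through.** **The plan's own figure.** Section 12.1 expects 15 to 40 monitored patients per cohort to treat 4, at 10 to 30% CXCL9 positivity. 4 / 0.30 = 13.3, rounded up to 14 (15 stated), and 4 / 0.10 = 40. This reproduces. The documents give no figure for GF frequency below threshold.

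**Are recently transplanted patients present at a hold?** The hold comes only after the cohort's last treated patient has finished, and treatment lasts up to 56 days (Section 5.4). Section 3.3 does not pause screening before then, so they can be expected.

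**Where the EoS visit falls.** EoS day = hold day + 0 to 7. Assume hold days spread evenly over Days 1 to 42 (or 1 to 98 in the last row).

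| EoS visit earlier than | EoS 7 days after hold | EoS same day |
|---|---|---|
| Day 21 | 13/42 = 31% | 20/42 = 48% |
| Day 42 | 34/42 = 81% | 41/42 = 98% |
| Day 98 | 90/98 = 92% | 97/98 = 99% |

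**How many are cut short.** The documents give no accrual time. If inclusion were steady over 6 to 12 months per cohort (an assumption), the share of a cohort within 42 days of HSCT at the hold would be 42/365 to 42/180 = 12 to 23%. Within 98 days it would be 98/365 to 98/180 = 27 to 54%. These are upper bounds on the share cut short, because some of these patients will be on treatment or already out of monitoring. Those with ANC at or above 500 will have moved on to monitoring for secondary GF only.

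**Implied true frequency.** Inputs are PPV 86% and sensitivity 90 to 100% (Section 1.1.2, HLH patients) and positivity 10 to 30% (Section 12.1). Applying them to this population is an assumption.

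GF below threshold = (positivity × PPV / sensitivity − positivity × PPV) / (1 − positivity)

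- Positivity 30%, sensitivity 90%: (0.2867 − 0.2580) / 0.70 = 4.1%
- Positivity 10%, sensitivity 90%: (0.0956 − 0.0860) / 0.90 = 1.1%
- Sensitivity 100%: 0%

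**Effect on the crude percentage.** Observed = f × (1 − h × m), where f is the true frequency, h the share cut short and m the share of their GF that is missed. With f = 4.1% and m = 1:

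| h | Crude frequency |
|---|---|
| 10% | 4.1 × 0.9 = 3.7% |
| 20% | 4.1 × 0.8 = 3.3% |
| 40% | 4.1 × 0.6 = 2.5% |

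The relative loss is h × m. The absolute loss in this range is at most about 1.6 percentage points. In events, even 40 below-threshold patients at 4.1% would have 1.64 expected GFs, and 20% cut short loses 0.33 of one.

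**The case against.** **No passage says that patients cut short count as free of GF.** Section 12.5.6 could be read the other way, since scoring an unobserved outcome as a non-event is itself a kind of imputation. Section 12.5 leaves full detail to a SAP, and no SAP text on this point appears in the material reviewed, so a censoring rule there cannot be excluded. This stands as a limit on certainty. The bias follows from the summary that the protocol states, not from an explicit scoring rule, but the protocol requires nothing that would prevent it.

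**Missed GF would usually leave a trace.** Section 10.1 says a second transplant is the only treatment once GF is confirmed and that death without one is almost certain. The calls to 3 years would pick up both. This partly stands: the evidence is collected, but it is indirect and falls outside the GF endpoints.

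**A reader might infer that all early exits bias this frequency.** The documents do not support that. The bars for infection, GvHD and relapse apply when treatment would start (Section 3.4.3), so those patients are above threshold and do not belong to this frequency. They do lose GF follow-up that matters to the correlation between CXCL9 and GF in untreated patients (Section 12.5.5). An exit for a second HSCT usually means that GF is already known.

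**The analyses are exploratory.** That is true, and the below-threshold frequency is not a listed endpoint. It limits the weight of the point but does not remove it.

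**Conclusion.** The concern holds for the crude GF frequency in untreated, below-threshold patients. The main route is the screening hold, and prohibited medication is the second. The direction is downward. The relative size is the share cut short times the share of their GF missed. Over the 0 to 4.1% range implied by the protocol's own figures, the absolute effect is small: a true 4.1% reads 3.7% to 2.5% with 10 to 40% cut short and all their GF missed. For a rule-out claim, the relative loss of up to 40% matters more.

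Two stronger readings should be avoided. The 12 to 54% shares rest on an assumed accrual time and describe patients who might be cut short; they do not measure the bias. Nor does the point reach the main efficacy endpoint, dose selection or the stopping guidance in Section 12.2, because patients on emapalumab continue per protocol at a hold.

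**What to change.** **Analysis (Sections 12.5.2 and 12.5.5, and the SAP).**

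- Estimate primary GF to Day 42 and secondary GF to Day 98 in untreated patients as cumulative incidence.
- Censor at the last joint GF and CXCL9 assessment. Below-threshold status is unknown after CXCL9 monitoring stops, and adding later GF without CXCL9 data could push the estimate too high.
- Treat death, and second HSCT for reasons other than GF, as competing events.
- Report how many patients were cut short by the hold and how many by prohibited medication.
- Do not restrict the analysis to patients who reached Day 42, engraftment or GF. That would keep early engrafters, drop patients still neutropenic at the hold, and bias the frequency low again.
- Censoring at the hold is administrative, but exit for prohibited medication may be informative. Add a sensitivity analysis that uses second HSCT, stem cell boost, DLI and death from the calls as a proxy for missed GF.

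This costs a few sentences of text and some tables, with no added visits.

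**Optional (Section 3.3).** Let patients in monitoring at the hold complete the ANC, CXCL9 and GF recording in Tables 5a and 5b to Day 42 or Day 98 before the EoS visit, with no change to who is treated. Chimerism would follow the schedule for the weight group; under 30 kg it is done only as clinically indicated. The cost is that sites and patients complete visits during the hold that the current text would drop. This must be settled before the first hold, because observations not made then cannot be recovered.

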3.4 Study periods

3.4.1 Screening Period

Screening starts with the signature of the informed consent by the patient or by the patient's legally authorized representative prior to any study-related procedures. It is the responsibility of the investigator/delegate to obtain written informed consent from each subject or legally authorized representative(s) after adequate face-to-face explanation of the objectives, methods, and potential hazards of the study.

It is permitted to re-screen patients once if the reason for non-eligibility was transient (e.g. abnormal laboratory test, insufficient wash-out period of a forbidden medication). All screening assessments must be repeated at the time of re-screening, except chest X-ray which should be repeated if older than 21 days. For patients below 30 kg, procedures performed during the screening period may be used to satisfy screening requirements if re-screening is performed within 21 days from the latest results.

Chest X-rays performed as part of medical practise prior to screening may be used to satisfy screening requirements if they are performed within the screening window of 21 days before HSCT.

Patients who have given written informed consent will undergo screening assessments between Day -21 and Day -8 prior to HSCT and will be assessed for eligibility to enter the study. Eligibility is also assessed prior to HSCT (Day 0). Patients will be stratified in order to include at least 40% of the patients with malignant and 40% with non-malignant disease (by means of an interactive response technology). Stratification will allow to explore the appropriate dose inhibiting IFN γ production in a similar number of patients presenting with malignant or non-malignant disease in each cohort. Assessments to be performed during screening are presented in the schedule of assessment (Table 5a and Table 5b).

A patient screening log will be maintained by the investigator for all eligible and non-eligible patients, with specification of reasons for non-eligibility, if applicable.

3.4.2 Allogeneic HSCT

Assessments to be performed on the day of HSCT are presented in the schedule of assessment (Table 5a and Table 5b) Patient's eligibility is assessed by checking inclusion/exclusion criteria prior to HSCT on Day 0. A patient is considered included in the study if he/she meets all inclusion/exclusion criteria prior to HSCT.

3.4.3 Monitoring and extended monitoring periods

Assessments to be performed during the monitoring periods are presented in the schedule of assessment (Table 5a and Table 5b).

See Table 2 and Table 3 for details on the transition from monitoring to extended monitoring, treatment and follow up in case of ANC < 500/ μ L (Table 2) and \geq 500 cells/ μ L (Table 3) during the monitoring period.

CXCL9 measurements will be performed by means of a validated assay on a device provided to the sites by Sobi AG. The exact CXCL9 threshold for treatment initiation will be provided in the CXCL9 assay laboratory manual.

Monitoring period

The monitoring period will start from the day after the HSCT (day 1) and will last until ANC is \geq 500 cells/ μ L or maximum until monitoring day 42 \pm 1, whichever comes first. During the monitoring period, CXCL9 and ANC measurements will be performed daily from day 1 up to day 7, every other day starting from day 9 until day 21 and every 3 days (\pm 1) starting from day 24 until day 42.

- If CXCL9 is measured above threshold and ANC is below 500 cells/ μ L, patients will enter the treatment period.
- If CXCL9 is measured below threshold and ANC is below 500 cells/ μ L, patients will continue the monitoring period until day 42 \pm 1 or until a second HSCT is planned.
- As soon as the ANC will be \geq 500 cells/ μ L during the monitoring period, patients will move to the extended monitoring period for secondary GF (sGF).

Extended monitoring period

The extended monitoring period will start as soon as the ANC will be equal or above 500 cells/ μ L during the monitoring period and will last maximum 98 \pm 3 days.

During the extended monitoring, CXCL9 and ANC measurements will be performed weekly up to day 98 \pm 3 days. In case of signs of sGF outside of the weekly visits, the patient should attend for an unscheduled visit and the assessments foreseen in the extended monitoring period visit should be performed to assess eligibility for treatment.

- If CXCL9 is measured above threshold and there are signs of sGF (i.e. donor chimerism drop of at least 10% for 2 consecutive measurements and/or ANC below 500 cells/ μ L and/or thrombocytopenia below 30000/ μ L not explained by any other reason than potential graft rejection), patients may optionally enter the treatment period, if the investigator will consider pre-emptive treatment with emapalumab the best option for the patient.
- If CXCL9 is measured below threshold, patients will continue the extended monitoring period until Day 98 \pm 3 days or until a second HSCT is planned.

Criteria not to start treatment during monitoring or extended monitoring

Patients presenting the following conditions at time of initiation of emapalumab treatment will not be eligible to receive emapalumab and will move to the phone-call follow-up period for non-emapalumab treated patients (see section 3.4.5).

- Uncontrolled infections (defined as clinically active infection regardless of treatment).
- Clinical manifestations of infections representing exclusion criteria (i.e. Atypical mycobacteria, Salmonella, Histoplasma capsulatum, Herpes zoster).
- Re-occurrence or progression of the underlying malignant disease based on medical judgment.
- GvHD.

